## 6.1. Screening Period

The screening period will be up to 28 days. Screening is the interval between the signing of the informed consent form (ICF) and the day the subject received the first dose of treatment in the study (Cycle 1 Day 1). Informed consent must be obtained before performing any study-specific procedures. Assessments that are required to demonstrate eligibility may be performed over the course of 1 or more days during this period.

Results from the screening visit evaluations will be reviewed to confirm subject eligibility before enrollment or the administration of study drug. Tests with results that fail eligibility requirements may be repeated once during the screening period if the investigator believes the results to be in error (eg, repeat biopsy allowed for subjects with a PD-L1 status of indeterminate when the PD-L1–low/negative NSCLC cohort is full, since the subject could be found to be PD-L1–positive with repeat biopsy). Additionally, a subject who fails screening may repeat the screening process 1 time if the investigator believes there has been a change in eligibility status (eg, after recovery from an infection).

## 6.2. Treatment Period

**Note:** As of Amendment 10, the option for monotherapy and re-treatment are only available to subjects who have already initiated monotherapy or re-treatment periods.

The treatment period with the combination therapy will continue every 21 days for up to 24 months, and then treatment with monotherapy INCB024360 may continue for up to 12 months if subjects are receiving benefit from treatment and have not had disease progression or met any criteria for study withdrawal, or subjects may stop both MK-3475 and INCB024360. Subjects who complete 24 months (35 administrations of MK-3475) of MK-3475, continue on monotherapy INCB024360 or stop both therapies, and later experience disease progression on INCB024360 monotherapy or off therapy may be considered for re-treatment with the combination for an additional 12 months (17 administrations of MK-3475) followed by the option to continue monotherapy INCB024360 for up to 12 months. Medical monitor approval is required for INCB024360 monotherapy treatment beyond 12 months.

### 6.2.1. Second Course Period (Re-Treatment Period)

Subjects who stop MK-3475 with SD or better may be eligible for up to 1 year of additional combination therapy if they experience disease progression after stopping the combination study treatment. This re-treatment is termed the second course period of this study and is only available if the study remains open and the subject meets either one of the following conditions.

- 1a. Stopped initial treatment of the combination after attaining an investigator-determined confirmed CR according to RECIST v1.1.
  - Was treated for at least 24 weeks before discontinuing therapy.
  - Received at least 2 cycles of the combination (2 doses of MK-3475 and at least 80% of the planned doses of INCB024360) beyond the date when the initial CR was declared.

**OR**

- 1b. Subject had SD, PR, or CR and stopped after 24 months (35 administrations of MK-3475) of study therapy for reasons other than disease progression or intolerability.

**AND**

2. Experienced an investigator-determined confirmed radiographic disease progression after stopping their initial treatment with MK-3475.
3. Did not receive any anticancer treatment since the last dose of MK-3475 other than INCB024360.
4. Have an ECOG performance status of 0 or 1.
5. Demonstrate adequate organ function as detailed in study inclusion criteria (Section 3.2).
6. Female subject of childbearing potential should have a negative urine or serum pregnancy test within 72 hours before receiving re-treatment with study medication.
7. Female subjects of childbearing potential (defined as women who have not undergone surgical sterilization with a hysterectomy and/or bilateral oophorectomy, and are not postmenopausal, defined as  $\geq 12$  months of amenorrhea) must have a negative serum pregnancy test. All female and male subjects of childbearing potential must agree to take appropriate precautions to avoid pregnancy or fathering children (with at least 99% certainty) from screening through 120 days after the last dose of study treatment. Permitted methods that are at least 99% effective in preventing pregnancy (see [Appendix A](#)) should be communicated to the subject and their understanding confirmed.
8. Does not have a history or current evidence of any condition, therapy, or laboratory abnormality that might interfere with participation for the full duration of the study or is not in the best interest of the subject to participate, in the opinion of the treating investigator.

Subjects who restart treatment will be re-treated with the 200 mg flat dose of MK-3475. For INCB024360, subjects should be treated at the same dose of INCB024360 they LAST received during the initial combination therapy (in particular, if a subject was dose reduced during initial combination therapy, he or she must resume second course at the same dose of INCB024360). Exceptions are noted below:

- If the subject was treated in Phase 1 with a dose lower than the recommended Phase 2 dose of INCB024360 (100 mg BID) as his or her initial treatment, AND did not require a dose reduction, he or she may begin second course treatment at 100 mg BID.

Treatment will be administered for up to 1 additional year.

Visit requirements are outlined in [Table 12](#) and [Table 13](#).

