### **9.4.3. Safety Analyses**

The principal analysis will be based on the safety evaluable population, according to treatment assignment.

Adverse events will be coded by the MedDRA, and incidences will be tabulated by preferred term and system organ class for all events, related events, events ≥ Grade 3 and adverse events of special interest. Severity of AEs will be based on the CTCAE scale as indicated in Section 8.1.1. Quantitative safety variables and their changes from baseline (laboratory, vital signs) will be summarized with descriptive statistics. Clinically significant abnormal values will be flagged and tabulated based on predefined criteria.

Exposure will be analyzed by describing dose intensity, which is defined as the dose-received divided by the dose planned over a given time interval. This will be done by cycle as well as overall cycles received for MK-3475 + INCB024360. The percentage of subjects with any delay and/or reduction will also be calculated.

The clinical laboratory data will be analyzed using summary statistics (eg, means and frequencies), and no formal statistical comparisons among the treatments are planned. In addition, these values will also be classified into CTCAE toxicity grades and tabulated. Descriptive statistics and mean change from baseline will be determined for vital signs at each assessment time. Vital sign results will be reviewed for clinically notable abnormalities.

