5.2. Treatment Groups

Subjects will be summarized overall and based on the dose regimen initially assigned:

- Pembrolizumab 2 mg/kg Q3W intravenously (IV) + epacadostat 25 mg BID
- Pembrolizumab 2 mg/kg Q3W IV + epacadostat 50 mg BID
- Pembrolizumab 2 mg/kg Q3W IV + epacadostat 100 mg BID
- Pembrolizumab 200 mg Q3W IV + epacadostat 300 mg BID
- Pembrolizumab 200 mg Q3W IV + epacadostat 50 mg BID (safety expansion)
- Pembrolizumab 200 mg Q3W IV + epacadostat 100 mg BID (safety expansion)
- Pembrolizumab 200 mg Q3W IV + epacadostat 300 mg BID (safety expansion)
- Pembrolizumab 200 mg Q3W IV + RP2D epacadostat (NSCLC PD-L1 high positive)
- Pembrolizumab 200 mg Q3W IV + RP2D epacadostat (NSCLC PD-L1 low/negative or indeterminate)
- Pembrolizumab 200 mg Q3W IV + RP2D epacadostat (Melanoma immune checkpoint-naive)
- Pembrolizumab 200 mg Q3W IV + RP2D epacadostat (Melanoma primary refractory)
- Pembrolizumab 200 mg Q3W IV + RP2D epacadostat (Melanoma relapsed)
- Pembrolizumab 200 mg Q3W IV + RP2D epacadostat (GU)
- Pembrolizumab 200 mg Q3W IV + RP2D epacadostat (TNBC)
- Pembrolizumab 200 mg Q3W IV + RP2D epacadostat (Ovarian cancer)
- Pembrolizumab 200 mg Q3W IV + RP2D epacadostat (SCCHN)
- Pembrolizumab 200 mg Q3W IV + RP2D epacadostat (DLBCL)
- Pembrolizumab 200 mg Q3W IV + RP2D epacadostat (RCC)
- Pembrolizumab 200 mg Q3W IV + RP2D epacadostat (MSI-high CRC)
- Pembrolizumab 200 mg Q3W IV + RP2D epacadostat (Gastric cancer)
- Pembrolizumab 200 mg Q3W IV + RP2D epacadostat (HCC)

Table summaries, unless otherwise indicated, will be provided by treatment group or tumor type.

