5.3.2. Safety Evaluable Population

The safety evaluable population will include all subjects enrolled in the study who received at least 1 dose of study drug. Treatment groups for this population will be determined according to the actual treatment the subject receives on Day 1. All safety analyses will be conducted using the safety population.

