6.4. Exposure

For subjects in the safety evaluable population, descriptive statistics will be provided by cohort; duration of treatment; average daily dose (mg) of epacadostat; and number of cycles of pembrolizumab.

- **Duration of treatment:** The number of study days between Day 1 and the last nonzero dose administration record of epacadostat or pembrolizumab taken by the subject.
- **Number of cycles of pembrolizumab:** The number of cycles of pembrolizumab for a subject will be the number of administered, scheduled infusions of pembrolizumab recorded on the MK-3475 Dosing eCRF.

Subjects who stop pembrolizumab with SD or better may continue on monotherapy INCB024360 for up to 12 months or stop both therapies; if these subjects later experience disease progression, they may be eligible for up to 1 year of additional combination therapy followed by the option to continue monotherapy INCB024360 for up to 12 months as long as they are receiving benefit from treatment or they may stop both therapies.

NOTE: Protocol Amendment 10 removed the option for monotherapy epacadostat and re-treatment combination treatment for any subject who has not already started initiated such treatment.

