8.2. Adverse Events

8.2.1. Adverse Event Definitions

A TEAE is any AE either reported for the first time or worsening of a pre-existing event after first dose of study drug. Analysis of AEs (as discussed below) will be limited to TEAEs, but data listings will include all AEs regardless of their timing to study drug administration.

Adverse events will be tabulated by the MedDRA preferred term and system organ class. Severity of AEs will be described and graded using the NCI Common Terminology Criteria for Adverse Events (CTCAE) v4.03. The CTCAE reporting guidelines and grading details are available on the Cancer Therapy Evaluation Program website (NCI 2010).

A grading (severity) scale is provided for each AE term. If the toxicity is not included in the CTCAE v4.03 criteria, it will be rated on a scale of 1 to 4 as follows: 1 = mild, 2 = moderate, 3 = severe, and 4 = life-threatening. All toxicities will be graded based on the worst level reached, not the level they may have reached if they had not been treated. When the intensity of an AE changes over time for a reporting period (eg, between visits), each change in intensity will be collected as an AE until the event resolves. Only the worst grade will be reported in AE summaries. Also, the Grade 3 or higher AEs will be reported in a summary table to display all higher-intensity AEs.

The subset of AEs considered by the investigator to be related to epacadostat or pembrolizumab will be considered to be treatment-related AEs. If the investigator does not specify the relationship of the AE to study drug, then the AE will be considered to be treatment-related. The incidence of AEs and treatment-related AEs will be tabulated. Serious TEAEs will also be tabulated.

Any missing onset date, causality, or severity must be queried for resolution. Unsolved missing values will be handled according to the following rules:

- An unsolved missing causality will be considered treatment related.
- An unsolved missing severity will be identified as an unknown severity.

For purposes of analysis, all AEs will be considered TEAEs unless the AE can unequivocally be defined as not treatment emergent. Therefore, an unsolved missing onset date will be considered treatment emergent, with the following exceptions:

- If the stop/resolution date is before the first dose administration date on Day 1, then the AE will be considered as not being treatment emergent.

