8.2.2. Adverse Event Summaries

An overall summary of AEs by treatment group will include the following:

- Subjects who had a TEAE
- Subjects who had a Grade 3 or higher TEAE
- Subjects who had a serious TEAE
- Subjects who had a fatal TEAE
- Subjects who had a TEAE leading to dose interruption of INCB024360
- Subjects who had a TEAE leading to dose interruption of MK-3475
- Subjects who had a TEAE leading to dose interruption of INCB024360 and MK-3475
- Subjects who had a TEAE leading to dose reduction of INCB024360
- Subjects who had a TEAE leading to discontinuation of INCB024360
- Subjects who had a-TEAE leading to discontinuation of MK-3475
- Subjects who had a TEAE leading to discontinuation of INCB024360 and MK-3475
- Subjects who had a treatment-related (INCB024360 or MK-3475) TEAE
- Subjects who had a INCB024360-related TEAE
- Subjects who had a MK-3475-related TEAE
- Subjects who had a Grade 3 or higher treatment-related (INCB024360 or MK-3475) TEAE
- Subjects who had a treatment-related (INCB024360 or MK-3475) serious TEAE
- Subjects who had a fatal treatment-related (INCB024360 or MK-3475) TEAE
- Subjects who had a treatment-related (INCB024360 or MK-3475) TEAE leading to dose interruption of INCB024360

- Subjects who had a treatment-related (INCB024360 or MK-3475) TEAE leading to dose interruption of MK-3475
- Subjects who had a treatment-related (INCB024360 or MK-3475) TEAE leading to dose interruption of INCB024360 and MK-3475
- Subjects who had a treatment-related (INCB024360 or MK-3475) TEAE leading to dose reduction of INCB024360
- Subjects who had a treatment-related (INCB024360 or MK-3475) TEAE leading to discontinuation of INCB024360
- Subjects who had a treatment-related (INCB024360 or MK-3475) TEAE leading to discontinuation of MK-3475
- Subjects who had a treatment-related (INCB024360 or MK-3475) TEAE leading to discontinuation of INCB024360 and MK-347

The following summaries will be produced by MedDRA term (if ≤ 10 subjects appear in a table, then a listing may be appropriate):

- Summary of Treatment-Emergent Adverse Events by MedDRA System Organ Class and Preferred Term
- Summary of Treatment-Emergent Adverse Events by MedDRA Preferred Term in Decreasing Order of Frequency
- Summary of Treatment-Related (Epacadostat or Pembrolizumab) Adverse Events by MedDRA System Organ Class and Preferred Term
- Summary of Treatment-Related (Epacadostat or Pembrolizumab) Adverse Events by Preferred Term in Decreasing Order of Frequency

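### SAP exposure and safety rules have no second-course split: off-drug gaps count as treatment, and re-treatment at 100 mg BID is tabulated under the lower starting dose (minor)

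*Protocol*

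**What the plan says.** Protocol 6.2.1 gives eligible subjects up to one further year of combination therapy, with pembrolizumab at 200 mg flat. Epacadostat normally restarts at the last dose received. The exception is a Phase 1 subject treated below 100 mg BID, who, under a condition on earlier dosing, has an option: "AND did not require a dose reduction, he or she may begin second course treatment at 100 mg BID".

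Treatment groups are fixed at the start:
- SAP 5.2: "Subjects will be summarized overall and based on the dose regimen initially assigned".
- SAP 5.3.2: "Treatment groups for this population will be determined according to the actual treatment the subject receives on Day 1".
- Protocol 9.4.3: "The principal analysis will be based on the safety evaluable population, according to treatment assignment".

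The analysis windows are:
- Duration (SAP 6.4): "The number of study days between Day 1 and the last nonzero dose administration record of epacadostat or pembrolizumab taken by the subject".
- Treatment-emergent events (SAP 8.2.1): "A TEAE is any AE either reported for the first time or worsening of a pre-existing event after first dose of study drug". No end is stated.
- Worst-value laboratory shifts (SAP 8.3.2): every postbaseline value is used, against the baseline before first dose (SAP 4.1.4).

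SAP 6.4 describes the second course but gives no rule for summarizing it. In Appendix E, re-treatment is separated only in dosing listings 2.5.4 and 2.5.5.

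**The concern.** Two things follow when these rules are applied as written.

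First, the duration formula is a single span. A subject who stops both drugs, progresses later and is re-treated has the off-drug interval counted as time on treatment. This applies to such a subject in either phase, whatever the second-course dose.

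Second, neither the adverse event nor the laboratory window closes or splits at the second course, while the group label stays with the starting regimen. A subject who took 25 or 50 mg BID first and 100 mg BID later contributes the higher-dose experience to the lower-dose column, with nothing in the table to show it. SAP 3.1 says that doses are not escalated within a subject, so a reader would have no reason to suspect it. Safety by dose is the main Phase 1 result, and the groups are small.

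**Working it through.** **Duration.** The SAP gives no worked figure to reproduce. Take 730 days for the first course (24 months, one of the two routes into re-treatment) and 91 or 365 days for the second (3 or 12 months). The gap is an assumption: 91 or 183 days. Overstatement = gap / days on drug.

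| Second course | Days on drug | Gap 91 days | Gap 183 days |
|---|---|---|---|
| 91 days | 730 + 91 = 821 | 91/821 = 11.1% | 183/821 = 22.3% |
| 365 days | 730 + 365 = 1095 | 91/1095 = 8.3% | 183/1095 = 16.7% |

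The range is about 8% to 22%. A subject who stayed on epacadostat alone between courses has no gap and no error.

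**Who can reach 100 mg BID.** Protocol Appendix K dates the exception to Amendment 9 (24 JAN 2018). Amendment 10 (02 JUL 2018) ended new re-treatment, 159 days later, plus site lag. Under Protocol 5.1.1 and 5.4, Amendment 10 also told melanoma subjects to stop epacadostat unless the medical monitor approved otherwise. The 12-month allowance for re-treatment already begun covers subjects without melanoma.

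**Average daily dose for one subject.** SAP 6.4 names this measure but gives no formula. I assume total dose / dosing days, with full dosing. The shortest first course for re-treatment is 168 days (24 weeks, with a confirmed complete response).

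- 50 mg BID safety expansion (100 mg/day assigned; melanoma only, 9 subjects by Protocol 4.1 and 4.1.1):
  - Low: (730×100 + 91×200)/821 = 111.1 mg/day. Shift in the mean of 9: 11.1/9 = 1.2 mg/day.
  - High, second course limited to 159 days: (168×100 + 159×200)/327 = 148.6 mg/day. Shift: 48.6/9 = 5.4 mg/day.
- 25 mg BID (50 mg/day assigned; 3 to 9 subjects by Protocol 9.2.1):
  - Low: (730×50 + 91×200)/821 = 66.6 mg/day. Shift: 16.6/9 = 1.8 to 16.6/3 = 5.5 mg/day.
  - High, subject without melanoma, 12-month second course: (168×50 + 365×200)/533 = 152.7 mg/day. Shift: 102.7/9 = 11.4 to 102.7/3 = 34.2 mg/day.

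The denominator matters. With 35 and 17 three-week cycles (735 and 357 days), a 25 mg BID starter averages (735×50 + 357×200)/1092 = 99.0 mg/day over dosing days. If a 180-day gap is left in the denominator, the figure is 108150/1272 = 85.0.

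**Event rates.** SAP 8.2.1 states: "Only the worst grade will be reported in AE summaries". A line such as "Subjects who had a Grade 3 or higher TEAE" therefore counts a subject once, and a second-course event changes it only if the first course had no such event. One added subject is then 1/9 = 11.1 points in a group of 9, or 1/3 = 33.3 points in a group of 3.

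**What does not move.** Dose-limiting toxicity closes at Study Day 42 (SAP 3.1.1), the recommended dose was chosen before the exception existed, and the efficacy tables in Appendix E cover Phase 2 only.

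**The case against.** Grouping by starting regimen is declared, and the same convention keeps dose-reduced subjects under their starting dose. The columns never claimed to show dose received. That stands: a reader might infer that the grouping itself is an error, and it is not. What is missing is any treatment of the second course within it.

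The windows are not all open-ended. Duration closes at the last nonzero dose, and the Protocol bounds event collection after treatment ends (42 days, or 90 for serious events). But for a re-treated subject the last dose falls in the second course, and Protocol 6.4.1 provides for a safety visit after each course. Neither limit separates the courses.

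Appendix E relies on Standard Safety Tables conventions that are not in these documents. A period rule could sit there, and listings 2.5.4 and 2.5.5 show that re-treatment dosing is identifiable. With adverse event listing 2.7.1, a reader could trace the events. That limits the harm but does not correct the tables.

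It is also tempting to end the main adverse event and laboratory tables at the first second-course dose. The documents do not support going that far. It would remove data from subjects re-treated at an unchanged dose, who are not mislabelled. It would also move late immune-related events, which Protocol 5.6.3 says may appear months after the last dose, out of the principal tables.

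**Conclusion.** The point holds, at minor severity. The duration rule is the firmer part: as written, it gives too long a figure for any re-treated subject with an off-drug gap, by about 8% to 22% under the gaps and course lengths assumed above. The by-dose part follows from the lack of a second-course split together with the starting-regimen groups; the SAP does not state the pooling outright.

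The number of affected subjects is not given and may be zero. The 100 mg BID option was optional, needed prior benefit followed by confirmed progression, and was open to new entrants for about 159 days.

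A reader might infer more in two ways that the documents do not support. One is that dose selection or the dose-limiting toxicity counts are contaminated; they are not. The other is that a full year at 100 mg BID is possible in the 50 mg BID expansion. That group is melanoma only, so without medical monitor approval the ceiling is about 149 mg/day for one subject and 5.4 mg/day for the mean of 9, apart from site lag. For 25 mg BID, the documents give 3 to 9 subjects, not a fixed 9.

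**What to change.** In SAP 6.4, compute duration of treatment and average daily dose separately for each course, exclude off-drug time between courses, and state the average-daily-dose formula.

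In SAP 8.2 and 8.3, keep the all-course adverse event and laboratory-shift tables. For subjects re-treated above their assigned dose, flag second-course events and shifts and show them in a supplementary table or listing by dose received. Add a note that late immune-related events may stem from the first course, and list the new output in Appendix E. If no subject was re-treated at a higher dose, say so in the study report.

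The cost is one date flag from dosing data already planned for listings 2.5.4 and 2.5.5, plus one small display or one sentence. No new data are needed.

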### **6.3. End of Treatment**

If a decision is made that the subject will permanently discontinue study drug, the EOT visit should be conducted. If the EOT visit coincides with a regular study visit, the EOT evaluations will supersede those of that scheduled visit, and the data should be entered in the EOT page in the eCRF. The subject should be encouraged to return for the follow-up visit.

